## I. PURPOSE OF THE STUDY AND BACKGROUND

#### Purpose

The purpose of the proposed study is to evaluate the effects of administering intravenous tranexamic acid (TXA) to patients undergoing anterior cruciate ligament (ACL) reconstruction with bone-patellar tendon-bone autograft to minimize hemarthrosis within the knee joint and post operative pain.

## **Rationale**

The anterior cruciate ligament (ACL) is the most common ligament injured in the knee, with as many as 246,000 tears occurring per year in the United States[7] Disruption of the ACL commonly occurs with a pivot-shift mechanism during athletic activity. Rupture of the ACL leads to anterior translation of the tibia with an associated impaction of the posterolateral tibial plateau against the midportion of the lateral femoral condyle. Upon impact, the articular cartilage overlying the bone marrow edema lesion is exposed to significant loads, potentially causing irreversible local injury and the release of pro-inflammatory, catabolic cytokines and chemokines into the joint space.[10, 14, 17] This acute phase of injury is characterized clinically by pain, an effusion and associated decreased knee range of motion.

ACL reconstruction is typically recommended in the young, active patient population in an effort to stabilize the knee and restore normal function. Bone-patellar tendon-bone autograft has shown to have the most successful outcomes. Several complications of both procedures include postoperative bleeding and swelling of the knee joint. There are two sources of bleeding after an ACL reconstruction including an intra-articular site and the donor site (extra-articular)[16]. Both sites can experience bleeding postoperatively leading to hemarthrosis and additional pain, which can prolong the recovery process. One technique utilized to reduce perioperative bleeding is the use of a tourniquet. Currently, other techniques are being tested to reduce perioperative bleeding. As a result, tranexamic acid (TXA) has been proposed as a solution to decrease these postoperative complications.

TXA is a synthetic anti-fibrinolytic agent that competitively inhibits the activation of plasminogen to plasmin by blocking tissue plasminogen activator and at higher concentrations directly inhibits plasmin[4, 9]. Plasmin, an enzyme that degrades fibrin clots, fibrinogen, procoagulant factors V and VIII[4]. Inhibition of plasmin decreases proteolytic action thus leading to clot formation and stabilization[4]. TXA is indicated in patients with hemophilia for short-term use (two to eight days) to reduce or prevent hemorrhage and reduce the need for replacement therapy during and following tooth extraction[13]. Administering TXA during the surgery will reduce the amount of plasmin in the system decreasing blood loss within and after the surgery. One gram of intravenous tranexamic acid (TXA) will be administrated before tourniquet inflation and before closure of the incision, as 1 g has been shown to be a safe amount with minimal side effects[16].TXA has already been shown to decrease perioperative bleeding in total knee arthroplasty and total hip arthroplasty, without increasing the risk of deep vein thrombosis[1, 2, 6, 8, 11, 15, 18].

This study is not being conducted under an IND number and will be conducted under IND exemption. This investigation is not intended to be reported to the FDA in support of a new

#### Version 2/26/20

indication for use nor support any other significant change in the labeling or advertising for the drug. The investigation does not involve a route of administration or dosage level or use in a patient population or other factor that significantly increases the risks (or decreases the acceptability of the risks) associated with the use of the drug product. The route of administration (IV) and dosage of 1 g has been shown to be safe and effective[13, 16]. The investigation is conducted in compliance with the requirements for institutional review set forth in part 56 and with the requirements for informed consent set forth in part 50; and The investigation is conducted in compliance with the requirements of 312.7.

We hypothesize that administration of TXA will reduce perioperative bleeding in BTB ACL reconstruction procedure with minimal side effects as compared to controls (no TXA). As a result, swelling and postoperative pain will decrease thus improving postoperative outcomes. By comparing two cohorts receiving the same procedure and administering TXA to one cohort, we can determine if the TXA affects perioperative bleeding and if decreasing perioperative bleeding will decrease postoperative pain and swelling.

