#### **Primary Objective**

The primary objective of the study is to determine if there are any differences in blood loss between patients undergoing BTB anterior cruciate ligament reconstruction who receive TXA compared to patients who do not receive it.

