#### **II. CHARACTERISTICS OF THE RESEARCH POPULATION**

#### Number of Subjects

We will aim to enroll a total of 110 subjects (55 per cohort) as determined by the priori sample size calculator.

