Information to be recorded pre-operatively includes age, sex, height, weight, BMI, and American Society of Anesthesiology (ASA) classification. Intra-operative information will also be recorded, including operative time, and estimated blood loss. During the surgery, a suction device is utilized to remove excess blood from the surgical site and sucked into the suction drain and placed into a measuring cup. We will measure the perioperative blood loss by looking at the measuring cup and seeing how much blood is inside. The objective is to have the average blood loss of the cohort receiving TXA less than the cohort not receiving TXA. Knee swelling postoperatively will be measured using the swelling ratio. The swelling ratio is defined as the circumference of the operative limb divided by the circumference of the contralateral limb. Pain severity scores at rest will be assessed by use of a visual analog scale (VAS; 0 = no pain, 10 =worst pain imaginable) at 0.5, 1, 1.5, 2, 4, 6, 24, and 48 hours as well as 7 days after surgery. Percocet consumption will be recorded at 24 hours, 1 day, 2 days and 7 days after surgery. Incidence of TXA-related side effects (nausea/vomiting, itching, anxiety, increased thirst, rapid heartbeat) in the first 24 hours will be noted. Time to discharge from the post-anesthesia care unit (PACU) and time to discharge from the hospital will be recorded. Patients will be in the study a duration of two weeks, until their post-operative follow up visit.

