#### **Data Analysis and Statistical Plan**

Statistical analysis will be performed using chi-squared and/or fisher's exact testing depending on size for binary variables. An a priori power analysis was conducted to estimate the minimum sample size needed to achieve 83% power (1 - b) at the .05 significance level which was calculated to be 50 patients. Therefore, we added 10 patients to account for potential exclusions, totaling 110 patients. Variables used in the power calculation were taken from the literature including an assumed effect size of 0.5 and standard deviation (SD) of 2. This large sample size will provide enough information to truly determine a difference between cohorts. This sample size and statistical analysis was used in similar studies looking at the effects of TXA in ACL

Version 2/26/20

reconstruction[5, 12].

Continuous variables will be compared with paired t-tests if the data is approximately normally distributed. If the data is not normally distributed, Mann-Whitney tests will be used. All protected health information will be removed prior to statistical analysis. We will use patient subjective pain, perioperative blood loss and knee swelling data as statistical endpoints. Subjective pain will be measured with the VAS (visual analogue scale), perioperative blood loss will be measured looking at blood loss from the suction drain after surgery. We are looking for a statistically significant difference in perioperative blood loss between the two cohorts. The swelling ratio is defined as the postoperative mean circumference of upper pole of patella and lower pole of patella divided by the preoperative values according to our previous study[9]. The endpoints must be statistically significant between the two cohorts to show TXA is effective.

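### The hypothesis of minimal side effects versus controls has no analysis that could support it; risk differences with confidence intervals would be a cheap improvement

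*Combined protocol and SAP*

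**What the plan says.** Four places bear on this point.

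- **Section I, Rationale.** The hypothesis is that TXA lowers perioperative bleeding "with minimal side effects as compared to controls (no TXA"). The word for minimal is not quantified, and no tolerable excess is given.
- **Section III, Methods and Procedures.** The data to be collected are described as follows: "Incidence of TXA-related side effects (nausea/vomiting, itching, anxiety, increased thirst, rapid heartbeat) in the first 24 hours will be noted". No expected rate is given for either arm.
- **Section III, Data Analysis and Statistical Plan.** The method for binary outcomes is "chi-squared and/or fisher's exact testing depending on size for binary variables". Side effects are not mentioned there. The endpoints named are pain, blood loss and swelling. No confidence interval, margin or precision statement appears.
- **Section I, Primary and Secondary Objectives.** These cover blood loss, then pain and swelling. Neither mentions safety.

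The planned size is stated in Section II: "We will aim to enroll a total of 110 subjects (55 per cohort").

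**The concern.** On its natural reading, the hypothesis says that side effects will be little or no more frequent with TXA than without it. A chi-squared or Fisher test takes no difference as its null hypothesis. It can show that side effects are more frequent with TXA, but failing to reject the null does not show that any excess is small. That would need an interval for the excess, or a test against a stated margin, and the plan has neither.

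At stake is what the trial can say about this part of its own hypothesis. With about 55 per arm, a non-significant comparison is likely even if a side effect is appreciably more common with TXA. A report giving only the p-value would not show the reader how large an excess remains possible.

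**Working it through.** **Inputs from the documents.** 55 per arm (Section II, Number of Subjects). Significance level 0.05 (Data Analysis and Statistical Plan). I took it as two-sided because the primary objective is to "determine if there are any differences in blood loss". The plan's stated minimum is 50 patients. I read this as per arm, because 2 × 50 + 10 = 110, and use 50 as a lower case should exclusions occur.

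**Assumed inputs.** All side-effect rates, because the documents give none. I used control rates from 5% to 30%.

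**The plan's own figure.** No power or precision is stated for side effects, so there is nothing to reproduce on this point. The only power figure is 83%, based on "an assumed effect size of 0.5 and standard deviation (SD) of 2". With a standardized effect of 0.5 and 50 per arm, I get 70.5% two-sided and 80.4% one-sided (normal approximation). Only one-sided testing at 55 per arm comes close, at 83.6%. That mismatch is a separate matter and does not enter the figures below.

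**Step 1: power of the planned test at n = 55 per arm.**
Power = Φ[(d − 1.96·SE0)/SE1], where d = p2 − p1, SE0 = √(2·p̄(1−p̄)/n), p̄ is the mean of p1 and p2, and SE1 = √((p1(1−p1) + p2(1−p2))/n).

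- 5% vs 10%: (0.05 − 1.96 × 0.0502)/0.0500 = −0.97, power 17%
- 10% vs 20%: (0.10 − 1.96 × 0.0681)/0.0674 = −0.50, power 31%
- 20% vs 40%: (0.20 − 1.96 × 0.0874)/0.0853 = 0.34, power 63%
- 30% vs 45%: (0.15 − 1.96 × 0.0923)/0.0912 = −0.34, power 37%

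The Fisher test, by exact enumeration, has lower power:

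| True rates | Chi-squared, 55/arm | Fisher, 55/arm | Chi-squared, 50/arm | Fisher, 50/arm |
|---|---|---|---|---|
| 5% vs 10% | 17% | 7.5% | 15.5% | 6% |
| 10% vs 20% | 31% | 22% | 29% | 19.5% |
| 20% vs 40% | 63% | 56% | 59% | 51.5% |
| 30% vs 45% | 37% | 30% | 34% | 27% |

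A true doubling from 5%, 10% or 20% would therefore be non-significant between 37% of the time (20% to 40%, chi-squared) and about 93% of the time (5% to 10%, Fisher) at 55 per arm.

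**Step 2: precision if the two arms have the same true rate p.**
Half-width of the 95% interval for the difference = 1.96·√(2p(1−p)/n).

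| p | 55 per arm | 50 per arm |
|---|---|---|
| 5% | 8.1 points | 8.5 points |
| 10% | 11.2 points | 11.8 points |
| 20% | 15.0 points | 15.7 points |
| 30% | 17.1 points | 18.0 points |

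**Step 3: what the interval adds to the p-value.** Two hypothetical results, TXA against control:

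- 5/55 vs 0/55: Fisher p = 0.057. The observed excess is 9.1 points, with a Newcombe 95% interval of about 0.8 to 19.6 points.
- 13/55 vs 5/55: Fisher p = 0.069, uncorrected chi-squared p = 0.039. The excess is 14.5 points. The Wilson limits are 0.144 to 0.363 and 0.039 to 0.196, so the Newcombe interval runs from 0.1455 − √(0.0927² + 0.1049²) = 0.005 to 0.1455 + √(0.1271² + 0.0514²) = 0.283, about 0.5 to 28 points.

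In the second case the two tests named in the plan fall on opposite sides of 0.05. In both cases the interval shows that an excess of 19 points or more is compatible with the data.

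**The case against.** The strongest reply is that the trial does not set out to answer a safety question. Blood loss, pain and swelling are the objectives and the endpoints. The side-effect phrase is a subordinate part of one sentence in the Rationale, and its comparison with controls could attach to the bleeding claim instead. Side effects are only to be noted, which suggests descriptive recording. The safety of the dose is argued from cited literature. The Data and Safety Monitoring Plan adds quarterly review and a stopping rule, and Section IV adds recovery-unit monitoring. The plan also gives no interval for any endpoint, and low power for adverse events is usual in a trial of 110.

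Much of this stands, and it keeps the point minor. It does not remove the gap: the hypothesis, on its natural reading, makes a comparative claim, data are collected that bear on it, and nothing in the analysis could support it. Monitoring and a stopping rule are not comparisons between arms.

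Three stronger readings are tempting, but the documents do not support them.

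- A reader might infer that the investigators will treat a non-significant result as proof of safety. No section says so. The one decision rule on significance concerns effectiveness.
- A reader might infer that the plan assigns chi-squared or Fisher tests to side effects. It assigns them to binary variables in general. Their use for side effects follows only because occurrence of a side effect is binary.
- A reader might take the upper limit for zero events in 55 patients, 1 − 0.025^(1/55) = 6.5%, as the excess that the trial can rule out. It bounds the rate in a single arm, not the difference from control, and applies only to events that do not occur at all.

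**Conclusion.** The point holds as a minor one. The plan hypothesizes minimal side effects relative to controls, and the only method that could apply to their incidence cannot support that claim. At 55 per arm the chi-squared test has about 17%, 31% or 63% power against a doubling from 5%, 10% or 20%. Even with identical true rates of 5% to 30%, the difference would be known only to within about 8 to 17 points, or 8.5 to 18 points at 50 per arm.

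The sizes depend on assumed side-effect rates, two-sided testing at 0.05, and all 55 (or 50) patients per arm being analysed. The conclusion does not depend on any single rate, since it holds across the range tried. The fault is a hypothesis without an interval, margin or interpretive rule. It is not an erroneous inference written into the plan, and it does not affect the primary analysis.

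**What to change.** - **Data Analysis and Statistical Plan:** report each side effect listed in Methods and Procedures by arm, as a count, a percentage and a risk difference with a 95% confidence interval (Newcombe, for example). State that a non-significant test will not be taken as evidence of minimal side effects.
- **Rationale:** reword the hypothesis so that side effects are estimated and compared descriptively. If precision is quoted, give the interval for the between-arm difference under stated assumed rates. Keep the 6.5% limit, if used at all, as a single-arm bound for events not seen in 55 patients.

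No margin has to be chosen, and no extra patients or data are needed. The cost is a few sentences, slightly more reporting and a more modest safety conclusion.

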#### Study Design

This will be a single-center, double-blinded randomized controlled study. The study is comparing blood loss and postoperative pain and swelling in two cohorts: patients undergoing BTB ACL reconstruction who receive TXA during surgery and patients who do not receive TXA. The intravenous tranexamic acid will be administered before surgery begins and after the tourniquet is released at the conclusion of the surgery. Blood loss will be measured via measuring the amount of blood in the drain at the conclusion of the surgery. Patients will be asked on postoperative day 1, 2 and 7 to rate their pain according to the VAS scale. Patients will have their knee swelling measured immediately postoperatively and at their one-week follow up visit. The swelling ratio is defined as the postoperative mean circumference of upper pole of patella and lower pole of patella divided by the preoperative values.[9]

#### **Primary Objective**

The primary objective of the study is to determine if there are any differences in blood loss between patients undergoing BTB anterior cruciate ligament reconstruction who receive TXA compared to patients who do not receive it.

#### Secondary Objective

Secondary objective of the study is to determine is there is a difference in post operative pain and swelling between patients undergoing BTB anterior cruciate ligament reconstruction who receive TXA and patients who do not receive it.

#### **II. CHARACTERISTICS OF THE RESEARCH POPULATION**

#### Number of Subjects

We will aim to enroll a total of 110 subjects (55 per cohort) as determined by the priori sample size calculator.

#### **Gender of Subjects**

Men and women will be included in this study.

Version 2/26/20

## Age of Subjects

Subjects included study will be aged 18-60 years, inclusive.

## **Racial and Ethnic Origin**

There are no enrollment restrictions based on race or ethnic origin.

### Inclusion Criteria

Patients will be screened for eligibility using the following criteria. All study subjects must meet the following inclusion criteria:

- Patients undergoing a BTB anterior cruciate ligament reconstruction
- Patients ages 18-60, inclusive
- •

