## **Exclusion Criteria**

Patients meeting the following criteria will be excluded from participation in this study:

- Legally incompetent or mentally impaired (e.g., minors, Alzheimer's subjects, dementia, etc.)
- Younger than 18 years of age
- Older than 60 years of age
- Any patient considered a vulnerable subject: pregnant women or fetuses, children, cognitively impaired adults, prisoners
- history of coagulation abnormalities and thromboembolic disease or current abnormal coagulation test values
- history of stroke or acute coronary syndromes within 3 months before surgery
- Preoperative (chronic) anticoagulation therapy
- Abnormal coagulation profile
- Renal failure (serum creatinine > 250 µmol/L [2.83 mg/dL]) or liver cirrhosis
- Sickle cell disease
- ACL reconstruction by a method other than BTB
- Patients with a history of hypersensitivity to Percocet and/or TXA
- •

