#### Version 2/26/20

medical histories will be performed based on their electronic medical records to identify any current pain medications or exclusion criteria. In order to maintain the blind, the resident assisting the surgeon will randomize the patient to one of two cohorts using REDCap. Both the resident and surgeon are members of the study team.

- Cohort 1: 1 gram of intravenous tranexamic acid (TXA) before tourniquet inflation and 1 gram of IV TXA before closure of the incision
- Cohort 2: Will not receive TXA.

The resident physician and anesthesiologist will not be blinded to the study, however the surgeon and study team members will remain blinded. Before the surgery begins, the resident will prepare the patient and the TXA will be administered (if assigned) before the tourniquet is placed, at which point the surgeon will be called into the room. The administration of TXA will not prolong the surgery and will not add any additional risks of prolonged anesthesia The surgeon will exit the surgery before closure at which point, the TXA will be administered (if assigned) and the resident physician will close the incision.

Immediate post-operative management will not be affected by this study. All patients will receive a standardized regimen of aspirin for DVT prophylaxis and Percocet for pain management, which is standard of care post-operative treatment.

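### Eligibility fixes only the graft type, and the plan neither names the operation mix (revision, combined) as data nor adjusts for it: some lost precision and an unseen case mix, not bias

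*Combined protocol and SAP*

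**What the plan says.** - **Rationale (section I):** the argument that a difference can be put down to TXA begins "By comparing two cohorts receiving the same procedure and administering TXA to one cohort".
- **Inclusion Criteria:** apart from age 18-60, the requirement is "Patients undergoing a BTB anterior cruciate ligament reconstruction".
- **Exclusion Criteria:** the only exclusion that concerns the operation itself is "ACL reconstruction by a method other than BTB". No section mentions primary versus revision status, or meniscal, cartilage or other ligament work.
- **Methods and Procedures, data items:** "Information to be recorded pre-operatively includes age, sex, height, weight, BMI, and American Society of Anesthesiology (ASA) classification". For the operation: "Intra-operative information will also be recorded, including operative time, and estimated blood loss".
- **Methods and Procedures, allocation:** "the resident assisting the surgeon will randomize the patient to one of two cohorts using REDCap". No stratification factor is given.
- **Data Analysis and Statistical Plan:** "We will use patient subjective pain, perioperative blood loss and knee swelling data as statistical endpoints". On the tests: "Continuous variables will be compared with paired t-tests if the data is approximately normally distributed", with Mann-Whitney otherwise. No covariate is named. Pairing does not fit two separate cohorts. That is a separate matter, and an independent-sample test is assumed below.

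**The concern.** A first-time isolated reconstruction, a revision, and a reconstruction with further work in the same knee all satisfy the criteria as written. The primary endpoint is the blood collected by suction, so the extent of surgery bears directly on what is measured. An effect on pain and swelling is plausible too, although the documents give no figures for any of the three.

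If operation type does affect the endpoints, two things are lost:
- **Precision.** The variation it causes stays in the error term of every unadjusted comparison.
- **Transparency.** A reader cannot see from the named data items what mix of operations was studied, or whether the cohorts had a similar mix.

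Operative time is the nearest named proxy. No analysis uses it, it is measured after the first TXA dose, and it cannot tell a revision from a slow primary operation.

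**Working it through.** **1. The plan's own figure.** Inputs from Data Analysis and Statistical Plan: 83% power, significance level 0.05, effect size 0.5, SD 2, n = 50. The 50 is read as per cohort because 2 × 50 + 10 = 110. With the effect size taken as a standardised d = 0.5 and an independent-sample t-test (noncentral t), power at 50 per cohort is 69.7% two-sided and 79.9% one-sided. The 83% is not reproduced. Two-sided, it needs 69 per cohort. One-sided, it needs 55, which is the enrolled number and leaves no allowance for exclusions. This gap is a separate problem and is not caused by case mix. The 69.7% serves here only as the baseline.

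**2. Share of variance due to operation type.** Let p be the share of combined or revision operations and s their outcome shift in within-type SDs. The documents give neither, so both are assumptions: p = 10% to 50%, s = 0.25 to 1.0.

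v = p(1 − p)s², R² = v / (1 + v)

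**3. Power after adjustment.** With d = 0.5 on the total SD, removing the operation-type variance gives d_adj = 0.5 / √(1 − R²). Two-sided, 0.05, 50 per cohort:

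| p | s | v | R² | d_adj | Power |
|---|---|---|---|---|---|
| none removed | – | – | 0 | 0.500 | 69.7% |
| 10% | 0.25 | 0.10 × 0.90 × 0.0625 = 0.0056 | 0.6% | 0.501 | 69.9% |
| 30% | 0.5 | 0.30 × 0.70 × 0.25 = 0.0525 | 5.0% | 0.513 | 71.9% |
| 50% | 0.5 | 0.50 × 0.50 × 0.25 = 0.0625 | 5.9% | 0.515 | 72.3% |
| 50% | 1.0 | 0.50 × 0.50 × 1.0 = 0.25 | 20.0% | 0.559 | 79.0% |

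The gain is about 0.2 points at the low end, about 2 in the middle and about 9 at the top. On 100 analysed patients, 100 / (1 − R²) makes this equivalent to about 101, 105 and 125 patients at the low, middle (30%, 0.5 SD) and top settings.

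**4. The other reading of the effect size.** If 0.5 is on the within-type SD, case mix multiplies the variance by 1 + v, which is 1.006 to 1.25. By the normal approximation, unadjusted power then falls from 70.5% to between 70.3% and 60.9%. The size is similar.

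**5. Chance imbalance.** With two independent binomial counts of 50, the probability that the cohorts differ by at least 10 percentage points in case mix is 13% (p = 10%), 33% (30%) or 37% (50%). For at least 20 points it is 0.2%, 4% or 6%. The 95% limit of the resulting shift in the mean difference is 1.96 × √(2p(1 − p)/50) × s:
- p = 10%, s = 0.25: 1.96 × 0.060 × 0.25 = 0.03 SD
- p = 50%, s = 1.0: 1.96 × 0.100 × 1.0 = 0.20 SD

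The planned effect is 0.5 SD. The test's error rate already allows for this variation.

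**The case against.** **Eligibility is read from silence.** No section says that revision or combined cases are admitted; the text only fails to exclude them. Both criteria lists end in an empty bullet, so a line lost when the PDF was read cannot be ruled out. This stands, and the point must be worded as not excluded. No other section supplies a restriction, so clarification is still needed.

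**The same-procedure statement may mean no more than BTB reconstruction in both cohorts.** That is a fair reading, and the criteria enforce it. The Rationale is therefore not contradicted. It just does not show how alike the operations are.

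**A reader might infer that the mix could never be examined.** The documents do not support this. The intra-operative list is worded as open-ended, charts are reviewed, and a link between study codes and record numbers is kept. Procedure type could probably be recovered. What is missing is a named field and a planned use for it.

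**A reader might infer from the imbalance probabilities that the comparison is biased.** It is not. Allocation is randomised, imbalance arises only by chance, and unadjusted tests remain valid.

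**The gain may be negligible, and adjustment is more than an added term.** Both stand. At 10% and 0.25 SD almost nothing is gained. Work first decided during surgery falls outside a covariate fixed beforehand, so 79.0% is an upper bound. Neither a t-test nor a Mann-Whitney test takes a covariate, so the main analysis would have to become a regression.

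**Conclusion.** The point holds as a matter of precision and reporting. The criteria restrict surgery only to BTB, the named data items include neither primary/revision status nor additional procedures, and the analysis is unadjusted. Enrolling all BTB reconstructions is a legitimate broad choice and is not criticised here.

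The benefit of adjustment ranges from almost nothing to at most about 9 points of two-sided power. That range rests wholly on the assumed 10% to 50% prevalence and 0.25 to 1.0 SD shift, with d = 0.5 on the total SD and 50 analysed per cohort. It should not be added to the gap between the stated 83% and the recomputed 69.7%, which arises from the sample-size calculation. The change is worth making because it is cheap, and because recording the mix has value even where adjustment gains little.

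**What to change.** 1. **Inclusion and Exclusion Criteria:** state whether revision and combined operations are eligible. This needs no change to who is enrolled.
2. **Methods and Procedures:** add primary/revision status, planned additional procedures (fixed before allocation) and performed additional procedures to the data items.
3. **Data Analysis and Statistical Plan:** for blood loss, VAS and swelling, pre-specify a linear model with treatment and planned operation type (isolated primary versus combined or revision), on a transformed or rank scale if the data are non-normal. Keep the unadjusted independent-sample test as a sensitivity analysis.
4. **Reporting:** tabulate performed procedures by cohort. Do not adjust for procedures decided during surgery, because that decision comes after the first TXA dose.

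Cost: two or three data fields taken from the booking and operative records, one degree of freedom, and a regression model in place of the simple two-group test as the main analysis. No extra patients or study procedures are needed.
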